5.6.3.4. Other Safety Parameters

5.6.3.4.1. Columbia Suicide Severity Rating Scale (C-SSRS)

The C-SSRS is a low-burden measure of the spectrum of suicidal ideation and behavior that was developed to assess severity and track suicidal events through any intervention (Posner K, Oquendo MA, Gould M, Stanley B, Davies M. Columbia Classification Algorithm of Suicide Assessment (C-CASA): classification of suicidal events in the FDA's pediatric suicidal risk analysis of antidepressants. Am J Psychiatry. 2007;164:1035-1043.). It is a clinical interview providing a summary of both suicidal ideation and behavior that can be administered during any evaluation or risk assessment to identify the level and type of suicidality present. The C-SSRS has been used frequently in clinical studies, and is a validated, standard measure for suicidal ideation assessment. Using the C-SSRS, the outcomes will be categorized using the scoring for the 11 categories:

Suicida	Suicidal Ideation (1-5)		
1	Wish to be dead		
2	Non-specific active suicidal thoughts		
3	Active suicidal ideation with any methods (not plan) without intent to act		
4	Active suicidal ideation with some intent to act, without specific plan		
5	Active suicidal ideation with specific plan and intent		
Suicida	Suicidal Behavior (6-10)		
6	Preparatory acts or behavior		

CONFIDENTIAL – FOIA Exemptions Apply in U.S.

4.1

NCT05307692

Statistical Analysis Plan 42847922 ALZ2001

1	Aborted attempt	
8	Interrupted attempt	
9	Actual attempt	
10	Suicide	
Non-suicidal self-injurious behavior (11)		
11	Non-suicidal self-injurious behavior	

At each time point, an event of suicidal ideation or behavior will be assigned a score of 1 to 10 based on the maximum response for the C-SSRS at that visit. If no events qualify for a score of 1 to 10, a score of 0 will be assigned (0="no suicidal ideation or behavior that can be assessed on the basis of C-SSRS"). A participant with an event of non-suicidal self-injurious behavior only will not be considered as having suicidal ideation or behavior; therefore, a score of 0 will be assigned. However, an additional score of 11 will be assigned to summarize any participants with an event of non-suicidal self-injurious behavior.

Shifts from baseline(DB) to the maximum score pertaining to suicidal ideation or suicidal behavior (i.e., scores 1 to 10) will be summarized by intervention for DB phase.

The maximum score (of scores 0 to 10) assigned to each participant will be grouped into one of three broad categories: No suicidal ideation or behavior (0), Suicidal ideation (1-5), Suicidal behavior (6-10). Shifts from baseline(DB) to the maximum category will be summarized by intervention for DB phase.

A frequency distribution of the scores for the 11 categories (0 to 10) will be provided by study intervention at each time point for DB phase. In addition, the number and proportion of participants with non-suicidal self-injurious behavior (a score of 11) will be provided by study intervention at each time point for DB phase.

5.7. Other Analyses

5.7.1. Pharmacokinetics

PK analyses will be addressed in a separate plan.

5.7.2. Actigraphy

Objective sleep parameters are measured using Actigraphy.

The device, Phillips Actiwatch Spectrum[®], is a wristwatch actigraphy system that provides accurate and objective activity, sleep, wake, and light-exposure data. Subjects will wear the device continuously during the screening and double-blind phases. Data will be downloaded and transmitted electronically to a study data file during study visits.

5.7.2.1. Analysis

The following parameters will be used for the analysis:

Parameter	Description
Total sleep time (min)	Number of scored sleep epochs, in minutes.

Statistical Anal	ysis Plan 4	2847922ALZ2001
------------------	--------------------	----------------

Parameter	Description
Number of wake bouts	A wake bout is an epoch or continuous epochs scored as
	awake
Sleep efficiency (%)	Scored total sleep time divided by total time in bed minus
	total invalid time, multiplied by 100.
Sleep onset latency (min)	Time between the start of a given rest interval and the
	following Sleep Start Time, in minutes.
Wake after sleep onset	Number of epochs of the given sleep Interval scored as
(min)	WAKE by the actigraphy software.
24 hour mean motor	The average of all valid physical activity counts for all
activity (counts/min)	epochs in a 24 hour period divided by the epoch
	length in minutes.
Daytime mean motor	The average of all valid physical activity counts for all
activity (counts/min)	epochs scored as ACTIVE divided by the epoch
	length in minutes.
Notes: An epoch is 30 to 60 s	econds.

The continuously collected data will be grouped into weekly intervals in the double-blind phase. Descriptive statistics of the mean weekly data (calculated based on non-missing daily data) and the change from baseline to each postbaseline time point in the double-blind phase will be presented by intervention group for the parameters listed in the table.

The change from baseline(DB) in each of the parameters will be analyzed using the same MMRM model as described for the primary endpoint with the respective baseline(DB) value as the covariate. The correlation between actigraphy parameters and the primary efficacy endpoint, SDI summary scores, and CMAI-C scores will be explored. Pearson and Spearman correlation coefficients will be calculated. Scatter plot of change in scores of the 2 assessment scales over time will be presented for each intervention group.

5.7.3. Biomarkers and Off-Body Sensor Data

Analysis of biomarker data will be discussed in a separate SAP. Analysis of off-body sensor data will be included in a separate plan.

5.7.4. Definition of Subgroups

Subgroup analyses of the primary endpoint will be performed for the full analysis set for the following subgroups:

Subgroup	Definition
Sex	Male
	Female
	Other
Age Group	Adult (<65 years)
	Elderly (≥ 65 years)
Age Group II	<65 years
	65-<75 years
	\geq 75 years
BMI	underweight (<18.5 kg/m2)
	normal (18.5-<25 kg/m2)
	overweight (25-<30 kg/m2)
	obese ($\geq 30 \text{ kg/m2}$)
Baseline NPI-12 sleep	<4
domain score (per eDC)	≥4

CONFIDENTIAL – FOIA Exemptions Apply in U.S.

6. SUPPORTING DOCUMENTATION

6.1. Appendix 1 List of Abbreviations

AD	Alzheimer's Disease
ADAS-Cog-14	Alzheimer's Disease Assessment Scale Cognitive subscale 14-item version
AE	adverse event
AESI	adverse event(s) of special interest
ALT/SGPT	alanine aminotransferase
ANCOVA	analysis of covariance
AST/SGOT	aspartate aminotransferase
ATC	anatomic and therapeutic class
BMI	body mass index
BPSD	Behavioral and Psychological Symptoms of Dementia
C-SSRS	Columbia Suicide Severity Rating Scale
CDR	Clinical Depression Rating
CI	confidence interval
CIR	copy increment from reference
CMAI-C	Cohen-Mansfield Agitation Inventory community version
CR	copy reference
CRF	case report form
CV	coefficient of variation
DB	double-blind
DSM-5	Diagnostic and Statistical Manual of Mental Disorders 5 th edition
ECG	electrocardiogram
eCOA	Electronic clinical outcome assessment
eDC	Electronic data capture
EW	Early Withdrawal
GDSI	Geriatric Depression Scale Informant version
IPA	International Psychogeriatric Association
IO	interquartile
IS	insomnia symptoms
IWRS	interactive web response system
LS	least squares
MAR	missing at random
MCMC	Markov Chain Monte Carlo
MedDRA	Medical Dictionary for Regulatory Activities
MI	multiple imputation
MMRM	mixed model for repeated measures
MMSE	Mini-Mental State Exam
MNAR	missing not at random
NPI-12	Neuropsychiatric Inventory – 12 item
NPI-12 A/A	Neuropsychiatric Inventory – 12 item Agitation/Aggression Domain
NPI-C	Neuropsychiatric Inventory – Clinician Rating
NPI-C A+A	Neuropsychiatric Inventory – Clinician Rating Agitation + Aggression Domains
NPI-C D+H	Neuropsychiatric Inventory – Clinician Rating Delusion + Hallucination Domains
PK	nharmacokinetic(s)
PWC-20	Physician Withdrawal Checklist-20
SAE	serious adverse event
SAP	Statistical Analysis Plan
SD	standard deviation
SDI	Sleep Disorder Inventory
SE	standard error
SNRI	selective noreninenhrine reuntake inhibitors
STUC	selective horepinepinine reupiake minorors

JNJ-42847922 (seltorexant)

NCT05307692

Statistical Analysis Plan 42847922ALZ2001

SSRI	selective serotonin reuptake inhibitors
TE	Treatment Emergent
TEAE	Treatment Emergent Adverse Event
TEMA	Treatment Emergent Markedly Abnormal
ULN	Upper limit normal

6.2. Appendix 2 Changes to Protocol-Planned Analyses

6.3. Appendix 3 Demographics and Baseline Characteristics

The number of participants in each analysis set will be summarized and listed by intervention group and overall. In addition, the distribution of participants by site ID will be presented unless otherwise noted.

Table 7 presents a list of the demographic variables that will be summarized by intervention group and overall for the full analysis set.

Table 7: Demographic Variables

Continuous Variables	Summary Type
Age (years)	Descriptive statistics (N, mean,
Weight (kg)	standard deviation [SD], median
Height (cm)	and range [minimum and
Body Mass Index (BMI) (kg/m ²)	maximum]).
Categorical Variables	
Age Group (Adult [<65 years], Elderly [≥65 years])	
Age Group II (55-64 years, 65-74 years, and \geq 75 years)	
Sex (male, female, unknown, undifferentiated)	
Race ^a (American Indian or Alaska Native, Asian, Black or African	
American, Native Hawaiian or other Pacific Islander, White, Multiple, Not	Frequency distribution with the
Reported)	number and percentage of
Ethnicity (Hispanic or Latino, not Hispanic or Latino, Not Reported,	participants in each category.
Unknown)	
BMI (underweight <18.5 kg/m ² , normal 18.5-<25 kg/m ² , overweight 25-	
$<30 \text{ kg/m}^2$, obese $\geq 30 \text{ kg/m}^2$)	

aIf multiple race categories are indicated, the Race is recorded as 'Multiple'

Table 8 presents a list of the baseline disease characteristics variables that will be summarized by intervention group and overall for the full analysis set.

Table 8: Baseline Disease Characteristics

Continuous Variables	Summary Type	
Baseline NPI-C A+A score		
Baseline NPI-12 total score	Descriptive statistics (N, mean,	
Baseline NPI-12 A/A domain score	standard deviation [SD], median	
Baseline NPI-12 sleep domain score per eCOA	and range [minimum and	
Baseline CMAI-C total score	maximum]).	
Baseline MMSE		
Categorical Variables		
Family history of diagnosed Alzheimer's disease or other cause of		
dementia		
Baseline NPI-12 sleep domain score category per eDC ($<4, \geq 4$)	Frequency distribution with the	
Community dwelling/assisted living per eDC	number and percentage of participants	
Baseline MMSE category (10 to 20, 21 to 24)	in each category.	
Baseline CDR score (1, 2-3)		

6.4. Appendix 4 Protocol Deviations

In general, the following list of major protocol deviations may have the potential to impact participants' rights, safety or well-being, or the integrity and/or result of the clinical study. Participants with major protocol deviations will be identified prior to database lock and the participants with major protocol deviations will be summarized by category for safety analysis sets.

- Developed withdrawal criteria but not withdrawn
- Entered but did not satisfy criteria
- Received a disallowed concomitant treatment
- Received wrong treatment or incorrect dose
- Other

Number of participants not meeting inclusion criteria, or meeting exclusion criteria will be summarized by study intervention group for the safety analysis set.

Additional analyses of protocol deviations for assessing and mitigating the impact of COVID-19 on study outcome are presented in Section 6.9.

6.5. Appendix 5 Prior and Concomitant Medications

Prior medications and concomitant medications will be coded using the World Health Organization Drug Dictionary (WHO-DD). Prior medications are defined as any therapy used before the day of first dose (partial or complete) of study intervention. Concomitant medications are defined as any therapy used on or after the same day as the first dose of study intervention, including those that started before and continue on after the first dose of study intervention.

Summaries of concomitant medications will be presented by ATC level 2 and ATC level 4 terms and base preferred term for the double-blind and follow-up phases for safety and follow-up analysis sets, respectively. The proportion of participants who receive each concomitant medication will be summarized as well as the proportion of participants who receive at least 1 concomitant medication. In addition, concomitant medications of special interest will be summarized. See Appendix 7 Medications of Special Interest for list of categories of medications of special interest.

Prior medications of special interest will be summarized by ATC level 2 and ATC level 4 terms and base preferred term.

6.6. Appendix 6 Adverse Events of Special Interest

AE Special Interest	Event Type
Category	
Somnolence	Somnolence
Cataplexy	Cataplexy
Sleep paralysis	Sleep paralysis
Complex, sleep-related	Confusional arousal
behaviors/parasomnias	Somnambulism
	Sleep terror
	Bruxism
	Sleep sex
	Sleep-related eating
	disorder
	Sleep behaviour disorder
	Catathrenia
Fall	Fall
Motor vehicle accident	Motor vehicle accident

6.7. Appendix 7 Medications of Special Interest

Categories for medications of special interest are defined as follows:

Medications of Special Interest		
Category		
Antidepressants		
Benzodiazepines		
Hypnotic/sedative including z-drugs		
Antipsychotics		
AChE inhibitors and memantine		
Aducanumab		
Non-Pharmacological Therapy		

6.8. Appendix 8 Criteria for Treatment-emergent Markedly Abnormal Laboratory Values

Laboratory Parameter	Unit	Low	High
Clinical Chemistry			
Albumin	g/dL	2.4	6.0
Albumin	g/L	24	60
Alkaline phosphatase	U/L	N/A	250
Alanine transaminase (SGPT)	U/L	N/A	200
Aspartate transaminase (SGOT)	U/L	N/A	250
Bicarbonate	mEq/L	15.1	34.9
Bicarbonate	mmol/L	15.1	34.9
Bilirubin (direct)	mg/dL	N/A	3.0
Bilirubin (direct)	μmol/L	N/A	51.3
Bilirubin (total)	mg/dL	N/A	3.0
Bilirubin (total)	umol/L	N/A	51.3
Blood urea nitrogen	mg/dL	N/A	50
Blood urea nitrogen	mmol/L	N/A	17.9
Calcium	mg/dL	6	12
Calcium	mmol/L	1.497	2.994
Chloride	mEq/L or mmol/L	94	112
Cholesterol	mg/dL	N/A	300
Cholesterol	mmol/L	N/A	7.758
Creatine kinase	U/L	N/A	990
Creatinine	mg/dL	N/A	3
Creatinine	umol/I	N/A	265.2
Gamma glutamyl transferase	U/L	N/A	300
Glucose Plasma	mg/dL	40	300
Glucose Plasma	mmol/L	2 204	16 653
High-density lipoprotein cholesterol (HDL)	mg/dL	35	N/A
High-density lipoprotein cholesterol (HDL)	mmol/L	0.905	N/A
Lactic acid dehvdrogenase (LDH)	U/L	N/A	500
Low-density lipoprotein cholesterol (LDL)	mg/dL	N/A	160
Low-density lipoprotein cholesterol (LDL)	mmol/L	N/A	4.1376
Phosphate	mg/dL	2.0	6.0
Phosphate	mmol/L	0.6458	1.9374
Potassium	mmol/L	3.0	5.8
Sodium	mEq/L	125	155
Sodium	mmol/L	125	155
Total protein	g/L	50	N/A
Total protein	g/dL	5	N/A
Triglycerides	mg/dL	N/A	500
Triglycerides	mmol/L	N/A	5.645
Uric acid	mg/dL	1.5	10
Uric acid	μmol/L	89.22	594.8
Hematology	•		
Hematocrit - female	%	28	50
- male	%	24	55
Hemoglobin	g/dL	8	19
Hemoglobin	g/L	80	190
Hemoglobin A1c	%	4	8
Neutrophils/Leukocytes	Fraction of 1	0.3	0.9
Monocytes/Leukocytes	Fraction of 1	N/A	0.2
Eosinophils/Leukocytes	Fraction of 1	N/A	0.1
Basophils/Leukocytes	Fraction of 1	N/A	0.06
Lymphocytes/Leukocytes	Fraction of 1	0.1	0.6
MCV	fL	40	140

-

NCT05307692

		Statistical Analysis Plan	42847922ALZ2001
MCH	pg	22	38
Reticulocytes/Erythrocytes	Fraction of 1	0.005	0.028
Platelet count	10 ⁹ /L; giga/L	100	600
Red blood cell (RBC) count - female	10 ¹² /L; tera/L	3.0	N/A
- male	10 ¹² /L; tera/L	3.0	N/A
White blood cell (WBC) count	10 ⁹ /L; giga/L	2.5	15.0
Urinalysis			
Urine pH		N/A	8.5
Urine specific gravity		< 1.001	> 1.035
Other			
Folate	ng/mL	4	4.8
B12	pmol/L	111	812

Note: Values should be flagged as markedly abnormally low if the value is less than the value indicated in the "Low" column. Likewise, values should be flagged as markedly abnormally high if the value is greater than the value indicated in the "High" column.

Note: The same limits apply to both males and females unless gender is indicated.

N/A = Not applicable.

6.9. Appendix 9 Analyses for Assessing and Mitigating the Impact of COVID- 19 on Study Outcome

The following measures will be taken to handle the impact of COVID-19 on study outcome:

- 1. Listing and summary of treatment discontinuations and study discontinuations including reasons due to COVID-19 will be presented.
- 2. Protocol deviations related to COVID-19 including missing visits and remote visits due to COVID will be summarized; corresponding listing will be provided.

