• If the postbaseline value is above the upper limit of the markedly abnormal criteria and the baseline(DB) value is equal to or below the upper limit, then the postbaseline marked abnormality will be considered TE. The same applies to the postbaseline value being below the lower limit of the markedly abnormal criteria with the baseline value being equal to or above the lower limit of the markedly abnormal criteria.

- Statistical Analysis Plan 42847922ALZ2001
- If the baseline(DB) value is missing, a postbaseline marked abnormality will always be considered as TE.

The number and percentage of participants with treatment-emergent markedly abnormal values in the double-blind phase will be presented by study intervention group.

The incidence of participants with treatment-emergent ALT values >3*upper normal limit (ULN) or AST value > 3*ULN will be presented for the double-blind phase. Additionally, incidence of treatment-emergent hepatic toxicity (suspected Hy's Law [U.S. Department of Health and Human Services, Food and Drug Administration, Center for Drug Evaluation and Research (CDER), Center for Biologics Evaluation and Research (CBER). [2009]] cases) defined as (ALT values >3*ULN or AST values > 3*ULN) AND total bilirubin values >2*ULN will be presented for the double-blind phase. Similar to the markedly abnormal analysis, only participants with baseline(DB) values that don't meet the criteria or are missing will be eligible for these analyses.

A listing of participants with treatment emergent markedly abnormal laboratory values will be provided. A listing of participants with ALT > 3* ULN or AST values > 3*ULN) and participants with hepatic toxicity (suspected Hy's Law cases) will be provided.

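### The folate limits in SAP Appendix 8 (low 4, high 4.8 ng/mL) make the treatment-emergent high flag uninformative, and the hematocrit low limits by sex need checking

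*SAP*

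**What the plan says.** SAP Appendix 8 sets a Low and a High limit for each laboratory parameter. Its notes say that "Values should be flagged as markedly abnormally low if the value is less than the value indicated in the" Low column, and that "values should be flagged as markedly abnormally high if the value is greater than the value indicated in the" High column. The rows that matter here are:

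- "Folate ng/mL 4 4.8"
- "B12 pmol/L 111 812", the only other analyte under the same Other heading
- "Hematocrit - female % 28 50", followed by a male row of 24 and 55
- "Hemoglobin g/dL 8 19", with no split by sex; the red-cell count floor is likewise 3.0 for both sexes

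SAP 5.6.3.1 turns these limits into treatment-emergent flags. A high flag requires a post-baseline value beyond High and also that "the baseline(DB) value is equal to or below the upper limit". The low side mirrors it, and a marked abnormality after a missing baseline always counts. The number and percentage of flagged participants are tabulated by intervention group, and a listing is produced.

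The SAP version 2.0 history records that some hematology limits were re-expressed as fractions and that the vitamin B12 limits were put into the correct units. It does not mention folate.

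**The concern.** A two-sided marked-abnormality limit should leave a broad middle range unflagged and pick out values well outside it. The folate row leaves 4.0 to 4.8 ng/mL and labels everything above that markedly high. Because the treatment-emergent rule also looks at baseline, the consequence is not simply too many flags. A participant who starts at or below 4.8 is flagged for a small rise, or for leaving the low zone. A participant who starts above 4.8 can never be flagged high, however large the rise. The high-side count would then mostly reflect where participants started, not what happened on treatment.

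Hematocrit raises a separate and weaker question. The high limits place men above women, while the low limits place men below women, and no reason is given.

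At stake is whether these rows of a by-arm safety table and its participant listing can be read as intended.

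**Working it through.** The limits are entered constants with no derivation in either document, so no stated calculation can be reproduced. The check applies the printed rules to test values chosen to show how the rules behave.

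**Rules** (SAP Appendix 8 notes and 5.6.3.1)

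- Treatment-emergent high: post-baseline > High, and baseline ≤ High or missing.
- Treatment-emergent low: post-baseline < Low, and baseline ≥ Low or missing.

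**Folate, Low = 4, High = 4.8 ng/mL**

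Unflagged band: 4.8 − 4 = 0.8 ng/mL.

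| Baseline | Post-baseline | Result |
|---|---|---|
| 4.5 | 5.0 | treatment-emergent high |
| 4.8 | 4.9 | treatment-emergent high |
| 3.5 | 5.0 | treatment-emergent high (a recovery from the low zone) |
| missing | 10 | treatment-emergent high |
| 10 | 12 | not counted |
| 10 | 40 | not counted, because baseline already exceeds 4.8 |
| 10 | 3.5 | treatment-emergent low |
| 3.5 | 3.0 | not counted, because baseline is already below 4 |

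The high/low ratio is 4.8/4 = 1.20, against 812/111 = 7.3 for B12. Most two-sided rows are at 1.7 or more. The exceptions are urine specific gravity (1.035/1.001 = 1.03), chloride (112/94 = 1.19) and sodium (155/125 = 1.24).

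**Is folate measured after baseline?**

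- Protocol exclusion criterion 9 refers to B12 and folate abnormalities at screening.
- Protocol Appendix 2 lists both under Others, apart from hematology and chemistry.
- The Schedule of Activities has no folate row. It shows hematology and chemistry together at screening, Day 1 and Day 43.
- SAP 5.6.3.1 plans descriptive and change summaries for chemistry, hematology and urinalysis, but applies the Appendix 8 limits to laboratory values in the double-blind phase.

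These entries do not settle the question.

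**Hematocrit, female 28 / 50, male 24 / 55 (%)**

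| Baseline to post-baseline | Woman | Man |
|---|---|---|
| 40 to 26 | treatment-emergent low | not counted |
| 40 to 23 | treatment-emergent low | treatment-emergent low |
| 45 to 52 | treatment-emergent high | not counted |

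The high limits run male above female by 55 − 50 = 5 points. The low limits run male below female by 28 − 24 = 4 points. If only the two low limits were exchanged, the 40 to 26 results would reverse. The 40 to 23 and 45 to 52 results would not change.

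**Glucose, mg/dL against mmol/L**

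The high pair implies a factor of 16.653/300 = 0.05551. Then 40 × 0.05551 = 2.220 mmol/L, against 2.204 as printed once the decimal point is restored. The gap is 0.016 mmol/L, and 0.016/0.05551 is about 0.3 mg/dL. Calcium, phosphate, creatinine, uric acid, LDL and triglycerides convert consistently.

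**The case against.** The strongest case against is that nothing in the documents proves any of these limits wrong. Neither document gives a folate or hematocrit reference range or the sponsor's standard. A narrow band is not decisive in itself, since chloride has almost the same ratio. If folate is drawn only at screening, the row produces no flags. Investigators must in any case review every laboratory report and record clinically relevant changes as adverse events (protocol 8.2.5). These points stand, and they limit the concern to how the rule behaves and to a request for verification.

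Three stronger readings are tempting, and the documents do not support them.

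- A reader might infer that the table flags ordinary folate values generally and misses real abnormalities. The baseline condition, "the baseline(DB) value is equal to or below the upper limit", means that participants starting above 4.8 are never counted as high. Falls from 4 or more to below 4 are caught. The failure is on the high side only, and without a reference range the documents cannot say which values are ordinary.
- A reader might infer that the hematocrit limits are transposed by sex. Only the low limits are out of order, and an unusual order is not proof of a swap. The common hemoglobin floor of 8 g/dL also gives men a second low red-cell flag.
- A reader might treat the glucose mismatch as a real error. In the text available, both mmol/L entries in that row have lost their decimal points, so a dropped character is a plausible cause. The gap would be immaterial even if real.

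The objection does not remove the folate problem. If the row is applied as printed, counting 3.5 to 5.0 as a marked abnormality and ignoring 10 to 40 is not useful under any reference range. That B12 needed correction in version 2.0, with no mention of folate beside it, is a further reason to check the row.

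**Conclusion.** The concern holds for the high side of the folate row. As printed, the treatment-emergent high flag depends on whether baseline was at or below 4.8 ng/mL or missing. It counts small or favourable rises and cannot register a rise from above 4.8. The low side works as intended. This rests on two assumptions: that the printed digits are those in the sponsor's file, and that folate is measured after baseline. If the second fails, the row has no effect.

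The hematocrit low limits are an ordering anomaly that merits verification, not an established error. What turns on it is the flagging of values from 24% to just under 28%, which now differs by sex. Glucose is trivial.

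The number of participants affected cannot be estimated, because the documents give no folate or hematocrit distribution. Only the descriptive treatment-emergent laboratory table and listing are touched. The efficacy analyses, significance level and sample size are not.

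**What to change.** Before database lock, in SAP Appendix 8:

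1. Replace the folate High entry with the upper limit in the sponsor's source standard, or with N/A if that standard has none, as is done for other one-sided analytes.
2. State whether folate is collected after baseline. If it is not, remove the row.
3. Check the hematocrit low limits by sex against the same standard, and change them only if an error is confirmed. If they are intended, a one-line note would prevent the question recurring.
4. Check the glucose low limit in mmol/L against its mg/dL row.

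The cost is a look-up in the source standard and at most a few table cells in the SAP and the matching programming specification. No data collection or efficacy analysis changes.
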